Symptomatic reactive hypoglycaemia is recognized in some patients with insulin resistance before the development of type 2 diabetes and is increasingly recognized as a complication of significant weight loss following bariatric surgery. Spontaneous hypoglycaemia is most commonly caused by an insulinoma which is a very rare diagnosis outside the context of MEN1 (1-4/million patients). In patients with MEN1, insulinoma is the second most common functioning pancreatic islet cell tumour (10-30%) (1) and typically occurs before the age of 40. In MEN1, the management of an insulinoma is the most challenging as: 1) Hypoglycaemia may be under reported as long term exposure to hypoglycaemia can result in hypoglycaemic autonomic failure with blunting or loss of the body's sympathetic response (loss of hypoglycaemic awareness) and an inability to counter-regulate subsequent or more serious events (2), including the possibility of sudden death (probably through cardiac arrhythmia) (3-5). 2) The chances of successful surgical resection and cure are lower as almost all MEN1 patients have multiple pancreatic lesions, many of which are smaller than the resolution of current imaging modalities. It can be difficult or impossible to know which lesion is producing insulin and extensive surgery can lead to pancreatic insufficiency to a degree that leaves the patient with extremely difficult to manage diabetes. As such patients are therefore often given medical therapies; these however are difficult to monitor for effectiveness, especially if there is loss of hypoglycaemic awareness.

Current testing limitations

Finger-prick glucose testing is currently the only viable way of home testing. Asymptomatic nocturnal hypoglycaemia is of most concern as repeat episodes are likely to lead to cumulative long term consequences of cerebral hypoglycaemia. Finger prick testing is unpopular amongst patients – it is painful and requires disposal

of 'medical sharps'. It also only provides a 'snapshot' of the patient's glycaemic state and so will, by its very nature; only provide this 'snapshot' when the patient is awake and able to use it.

Continuous glucose monitoring

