6.3 Primary endpoint

Arm 1 -

Outpatient - CGM findings reflect patient's fingerprick glucose readings

- Episodes of true hypoglycaemia (as decided by finger prick glucose testing) are captured by the CGM device

- CGM detects hypoglycaemia whilst patient is asleep

Inpatient - 72 hour fast - CGM device calls hypoglycaemia when fingerprick/lab glucoses also do

Arm 2 -

Blinded phase - CGM findings reflect patient's fingerprick glucose readings - any episodes of true hypoglycaemia (as decided by fingerprick glucose testing) are captured by CGM device

unblinded phase - CGM recordings help with titration of anti hypoglycaemic medications and this reduces overall incidence of hypoglycaemic episodes or duration of time spent in hypoglycaemic range

For patients experiencing asymptomatic hypoglycaemic episodes, a reduction in asymptomatic hypoglycaemic episodes and regaining of hypoglycaemic symptoms.

For patients with symptomatic hypoglycaemia, a reduction in symptomatic episodes.

7. Study population

Clinicians in the endocrinology department at St Bartholomew's hospital will be notified of this study and encouraged to refer forward suitable patients from their clinics.

Arm 1

Patients referred to the endocrinology department at St Bartholomew's hospital for investigation of suspected hypoglycaemia by either GPs or other clinical teams in the same or external NHS trusts will be referred onwards to the study team by the doctor that sees them for their routine clinical care.

Arm 2

Patients known to the endocrinology department at St Bartholomew's hospital with hypoglycaemia that are medically managed or who are to start medical management will be referred to the study team by the doctor that sees them for their routine clinical care.

Some patients who are found to have hypoglycaemia through arm 1 of this study will be automatically offered the chance to partake in arm 2 if they are to have medical treatment.

No vulnerable groups will be included – all patient will be able to give valid consent on their own behalf
All patients will be able to understand sufficient English to give informed consent on their own behalf.

Inclusion Criteria

Able and willing to give informed consent. No vulnerable adults will be included.
Either conventional gender, or non-binary.
Age >18 years
Any ethnicity
Any socio economic group
Medical condition as detailed above – arm 1 under investigation for possible/probable hypoglycaemia

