12.2 Method of analysis

P<0.05 will be considered statistically significant

Arm 1

Positive and negative predictive value of CGM diagnosis of hypoglycaemia as an outpatient or an inpatient vs 72 hour fast (considered the 'gold standard')

Arm 2

In each patient, comparison of number of episodes of hypoglycaemia by finger prick glucose vs CGM vs symptoms during CGM blinded phase.

Severity of hypoglycaemia excursions

Amount of time spent in the hypoglycaemic range after medication titration – as measured by area under the curve on a time vs glucose graph generated by CGM machine. Comparisons of mean hypoglycaemic frequency and time within hypoglycaemic range within patients (blinded vs unblinded phase) using paired T test.

Change in hypoglycaemia questionnaire score before/after CGMs monitoring and medication titration

Regain of symptomatic hypoglycaemia in patients with asymptomatic hypoglycaemia, reduction of symptomatic hypoglycaemia in other patients.

13. Ethics

- Informed consent

Patients will be offered the chance to partake in the study should their treating consultant feel that they meet the inclusion criteria. Declining an invitation to take part in the study or leaving at any time means that the patient will default back to standard of care investigations. Their care will not be prejudiced or compromised in any way through either taking part or not taking part in the study.

- Recruitment

Only patients under investigation/treatment for hypoglycaemia at St Bartholomew's hospital will be considered for entry to the study. Patient being treated/investigated elsewhere who wish to be considered for the study would need to have their care transferred to St Bartholomew's by their GP/current endocrinologist.

- Inclusion / exclusion criteria

Inclusion/exclusion criteria is intended to screen out patients who have conditions that may affect their blood glucose (Diabetes Mellitus, underlying hepatic pathology) or in whom CGM is not recommended (pregnancy, critical illness) or in whom hypoglycaemia may be caused by extrinsic factors such as Diabetes medication.

- Study design

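### The Arm 2 item for symptomatic patients can be met through loss of awareness as well as through fewer lows, and sections 6.3 and 12.2 group the patients differently

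*Protocol*

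**What the plan says.** Protocol section 6.3 gives three items for the unblinded phase of Arm 2.

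- The overall item, for the phase as a whole: CGM data guide titration, with the result that "this reduces overall incidence of hypoglycaemic episodes or duration of time spent in hypoglycaemic range".
- The asymptomatic item, for anyone whose lows go unfelt: fewer silent lows, together with a return of warning symptoms.
- The symptomatic item, worded in full as: "For patients with symptomatic hypoglycaemia, a reduction in symptomatic episodes".

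The second item has two parts. The third has one, with no condition on silent or total episodes.

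Section 12.2 carries the last two into the analysis as "Regain of symptomatic hypoglycaemia in patients with asymptomatic hypoglycaemia, reduction of symptomatic hypoglycaemia in other patients". It names no test for them. The test it names for Arm 2 concerns the first item: "Comparisons of mean hypoglycaemic frequency and time within hypoglycaemic range within patients (blinded vs unblinded phase) using paired T test". It also lists change in the hypoglycaemia questionnaire score.

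On the link between lows and symptoms, section 5 (Pathophysiology and significance of hypoglycaemia) says that "long term exposure to hypoglycaemia can result in hypoglycaemic autonomic failure with blunting or loss of the body's sympathetic response". Section 5.4 adds that symptoms are not always a dependable guide, because awareness can be lost.

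**The concern.** A count of symptomatic episodes mixes two quantities: how many lows occur, and what share of them the patient feels. A fall in the count is good news only if it comes from the first. By the Protocol's own account the second can also fall, and that is a harm: section 5.5 lists elimination of dangerous asymptomatic hypoglycaemia among the expected benefits. As worded, the item cannot tell the two routes apart, so a primary-endpoint item could be reported as met while hypoglycaemia is unchanged or worse.

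The grouping adds a second problem. In 6.3 a patient with both felt and silent lows fits both of the last two lines. If silent lows become felt, the asymptomatic line counts this as success and the symptomatic line counts it as failure.

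**Working it through.** **Inputs.** The Protocol gives no episode rates, no felt share and no expected effect. Section 12.1 gives 30 patients as a pilot. There is therefore no figure of the plan to reproduce. All rates below are assumed, over equal observation time before and after.

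**Formula.** Let N be the number of lows and a the share felt. Symptomatic episodes are S = N × a and silent episodes are N − S. The item is met when S2 < S1, that is, when a2/a1 < N1/N2. It is therefore met once the felt share falls, in relative terms, by more than 1 − N1/N2:

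- lows unchanged: any fall in the felt share
- lows × 1.2: 1 − 1/1.2 = 17%
- lows × 1.5: 1 − 1/1.5 = 33%
- lows × 2.0: 1 − 1/2.0 = 50%

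**Cases.** Before: 10 lows, 80% felt, so 8 symptomatic and 2 silent.

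| Case | Lows after | Share felt | Symptomatic | Silent | Symptomatic item | Total lows |
|---|---|---|---|---|---|---|
| a | 10 | 40% | 4 | 6 | met | unchanged |
| b | 15 | 40% | 6 | 9 | met | up |
| c | 15 | 25% | 3.75 | 11.25 | met | up |
| d | 15 | 60% | 9 | 6 | not met | up |
| e | 5 | 80% | 4 | 1 | met | down |

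Cases a and e give the same result on the item (8 to 4, a 50% fall). In e the lows are halved; in a they are unchanged and silent lows treble.

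**Chance variation.** With Poisson counts at these rates (400,000 simulated patients per case), the symptomatic count falls in 87% of patients in case c and 65% in case b. The total count falls in about 13% in both, so the overall count would usually expose the worsening. If the expected total stays at 10, as in case a, it falls by chance in about 45%. Time in range was not simulated.

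**Mixed patients.** Reverse case a: 10 lows in each period, felt lows rising from 4 to 8, silent lows falling from 6 to 2. Under 6.3 the asymptomatic line is met (6 to 2, symptoms regained) and the symptomatic line is not (4 to 8). Under 12.2, "reduction of symptomatic hypoglycaemia in other patients" takes this patient out of the symptomatic line, so the conflict does not arise there. The two sections treat the same patient differently.

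**Patients with no silent lows at the start.** Take 10 lows, all felt, followed by 10 lows of which 4 are felt. Symptomatic episodes fall from 10 to 4 and silent lows rise from 0 to 6. If groups are set at the start, 12.2 places this patient among the others and does not apply the asymptomatic line. The Protocol does not say when patients are classified.

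**The case against.** A reader might infer that a patient who gets worse is scored as a success. The Protocol does not support that. It has no patient-level scoring rule, and the symptomatic line is one of three items. Overall incidence or time in range applies to the whole unblinded phase and is analysed by paired t test. The patient in case a shows no fall in total lows. Having had 2 silent lows before, that patient also falls under the asymptomatic line of 6.3 and fails it. The example therefore shows items that disagree, not a worsening patient passed overall. This stands.

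The time scale also weakens the stronger reading. Section 5 ties blunting to long-term exposure, whereas Arm 2 has at most 10 + 20 = 30 days of CGM, during which treatment is adjusted to remove lows. Nothing in the Protocol shows how often awareness would newly be lost in that window. This stands as a limit on size. It does not remove the point, because 6.3 itself expects awareness to change in the other direction, and the questionnaire is repeated at up to 6 months.

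It can also be said that a statistical analysis plan may settle how items combine, and that 12.2 already resolves mixed patients. The first is possible, but the unguarded item is fixed in the Protocol's own primary endpoint. The second is right as far as it goes. Yet the same wording removes the asymptomatic check from a patient who starts with felt lows only, and 6.3 still reads differently. Nor does the overall item act as a guard: no rule links it to the symptomatic one, and because it is met by fewer episodes or by less time, it can be met with the number of episodes unchanged.

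**Conclusion.** The point holds in a limited form. The symptomatic item in 6.3 and 12.2 can be met through loss of awareness, because it is not tied to total or asymptomatic CGM-recorded episodes and the Protocol does not say how it combines with the overall item. The logic needs no assumed rates. The illustrated size (a 50% symptomatic fall with lows unchanged, or an item still met when lows rise 1.5 times and the felt share drops by more than 33%) rests entirely on assumed figures. The frequency within the trial is unknown. What is affected is this item, not necessarily the endpoint as a whole. The overlap of groups in 6.3 against exclusive groups in 12.2 is an inconsistency visible in the text itself.

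**What to change.** In 6.3 and 12.2:

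1. State that a fall in symptomatic episodes counts as benefit only if total CGM-recorded episodes also fall. The total is the overall-incidence measure already listed and analysed. Under this rule cases a, b and c no longer meet the item, and case e still does.
2. Report the symptomatic share of episodes beside it, as a measure of awareness.
3. Use the same mutually exclusive groups in both sections, with patients who have both kinds of episode placed in one named group.

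The cost is wording only. CGM already records the lows and the diary (section 17.3) already has a place for symptoms, so no new data are needed and no clinical rule changes. The symptomatic item becomes slightly harder to meet.

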7.1 Inclusion criteria

Able and willing to give informed consent. No vulnerable adults will be included.
Either conventional gender, or non-binary.
Age >18 years
Any ethnicity
Any socio economic group
Medical condition as detailed above – arm 1 under investigation for possible/probable hypoglycaemia
Arm 2 – on medical therapy for established hypoglycaemia

7.2 Exclusion criteria

Unwilling or unable to give consent
Unable to speak sufficient English to give consent and understand study requirements
Age<18
Lack of capacity to consent
Underlying hepatic condition

Current excessive alcohol consumption (men regularly consuming >50 units/week, women >35 units/week)

Current use of Diabetic medication or insulin

Currently pregnant

Any patient on haemo or peritoneal dialysis

8. Study design

Arm 1

Patients will be recruited to the study via the endocrine outpatient clinic, or via referral to St Bartholomew's hospital for inpatient management of hypoglycaemia.

For those originating from the outpatient department, patients will receive a CGM kit, finger prick testing meter and glucose monitoring diary.

5 days prior to admission to hospital the patient will start the continuous glucose monitoring and will also record their finger prick glucose reading in their glucose monitoring diary at any point they experience symptoms they ascribe to hypoglycaemia.

During their admission to hospital for investigation into suspected hypoglycaemia (either patients from outpatients, or direct admissions), patients will continue/start continuous glucose monitoring, alongside standard of care twice daily venous glucose, insulin and c-peptide measurements and routine finger prick testing. As per standard of care, extra finger prick glucoses and venous glucose/insulin/c-peptide testing will be performed when the patient experiences symptoms that they associate with hypoglycaemia.

Arm 2

Patients who have been diagnosed with spontaneous hypoglycaemia which requires medical therapy will be given a CGM kit and a finger prick glucose monitoring device and glucose monitoring diary. Patients will take the standard medical therapy and perform finger prick glucose testing when they experience symptoms that they attribute to hypoglycaemia. These values will be recorded in the glucose monitoring diary. After (up to) 10 days of blinded CGM monitoring, the diary and CGM data will be reviewed. A member of the endocrine team (consultant or registrar with consultant approval) will then make changes to the medical therapy in order to abolish any remaining episodes of hypoglycaemia. Patients will then wear the CGM device in unblinded mode for up to a further 20 days (though likely to be far less) in order to facilitate further medication titrations. Patients will be asked to confirm low CGM glucose readings during this time with a finger prick glucose measurement.

The study organisers will observe the glucose data obtained from the CGM and match it with finger prick glucose readings (from glucose monitoring diaries) and lab glucose data to check for concordance.

CGM data (in conjunction with glucose monitoring diaries) will be scrutinised and compared against drug regimens to see which doses needed to be altered, or where additional medication is required.

Patients will complete a modified Clarke and Gold hypoglycaemia questionnaire at the start of arm 2. They will complete an adapted questionnaire prior to surgery for their hypoglycaemia (if indicated) or at 6 months after the start of arm 2 – whichever comes first.

9. Study procedures

Arm 1

Patients will be recruited either through attendance at endocrinology outpatients at St Bartholomew's hospital or through inpatient transfer to St Bartholomew's hospital – both with suspected diagnoses of hypoglycaemia.

If attending the outpatients department with suspected hypoglycaemia and thought to be suitable for the study, then the patient will meet a member of the study team after their outpatient appointment or they will be offered an appointment to discuss the study at a mutually convenient time. Informed consent will be obtained during this meeting.

Once a date has been set for their admission to hospital for standard of care investigation of hypoglycaemia (usually including an oral glucose tolerance test or mixed meal test, but certainly including a 72 hour fast), an appointment will be made with the patient for 5 days prior to this date.

At this appointment, the patient will be provided with a finger prick glucose monitoring kit (and instructed in how to use it), a glucose monitoring diary to record finger prick glucose measurements and a CGM device. A CGM probe will be fitted during the consultation and checks made to ensure that it is working.

The patient will then proceed with their standard of care admission five days later. CGM monitoring will continue for the duration of their admission. The CGM device will be removed at discharge or after 5 days of admission, whichever comes first.

For patients who are transferred to St Bartholomew's directly for investigation of their hypoglycaemia, informed consent will be obtained at the earliest convenient point in their admission and the CGM device applied in preparation for the standard of care investigations. The CGM device will be removed at discharge or after 5 days of admission, whichever comes first.

Schedule of study interventions

Study intervention	Visit 1	Visit 2	Visit 3
Establishment of possible hypoglycaemia diagnosis	x		
Meet with study team to learn about study and give Informed consent	Either x	Or x	
Placement of CGM device, receive finger prick glucose meter and diary		x	
Admission to hospital for standard of care investigations Return CGM receiver device if not proceeding to arm 2			x

Arm 2

For patients with confirmed hypoglycaemia, where it is planned that they will receive medical management, we will seek informed consent for their entry into arm 2 of the study.

This might take place;

- at the conclusion of inpatient investigations for hypoglycaemia prior to initiation of anti-hypoglycaemia medication (on an inpatient or outpatient basis)
- after an endocrinology outpatient appointment for a patient with confirmed hypoglycaemia

In the first instance, patients will be fitted with a CGM device and given a finger prick glucose monitoring kit and glucose monitoring diary. Each patient will be asked to complete a modified Clarke and Gold hypoglycaemia questionnaire.

A further appointment will then be made to discuss the results of the initial CGM and to titrate the drug regimen. This appointment could be face to face or by telephone.

If periods of hypoglycaemia persist then alterations to the drug regime will be made and the patient will continue to wear the CGM device, but both they and the investigators will be unblinded to the CGMs allowing further titrations to the anti-hypoglycaemia medications to be made by telephone. Patients will be asked to take a finger prick glucose reading to confirm any low CGM readings.

At the conclusion of the patient's study participation, they will be asked to return the CGM receiver.

At 6 months, or prior to surgery to cure the hypoglycaemia (whichever comes first) the patient will attend the hospital to complete an adapted version of the modified Clarke and Gold hypoglycaemia questionnaire.

Schedule of study interventions

Study intervention	Visit 1	Visit 2	Visit 3	Visit 4	Visit 5
Meet with study team to learn about study and give Informed consent	x				
Placement of CGM device, receive finger prick glucose meter and diary Complete hypoglycaemia questionnaire	Either x	Or x			
Review of CGM data and titration of medication and unblinding of CGM device		Either x	Or x		
Subsequent medication titration by telephone			Either x	Or x	
Return CGM receiver device				x	
Complete adapted hypoglycaemia questionnaire					x

Study Drugs/device

The drugs used to treat hypoglycaemia will be those that are current standard of care and the doses/indications will not vary from standard practice.

We will use a Dexcom G6 continuous glucose monitoring device to record patient's blood glucose to aid diagnosis of hypoglycaemia prior to and during standard of care hospital investigations. The device's software will be modified by Dexcom to disable hypoglycaemia alarm functions, visible blood glucose readout (on the receiver device) and the ability to view blood glucose remotely.

For the unblinded component of arm 2 these functions will be restored

Concomitant medications

Patients will continue to take all other prescribed medications.

Criteria for discontinuation

Patients that become pregnant, or develop a critical illness during the study will be withdrawn as Dexcom devices are unreliable in these circumstances.

Procedure for data collection

Arm 1 – CGM data from each Dexcom device will be downloaded at the end of the inpatient investigations.

Finger prick Glucose monitoring diaries will be collected from patients.

Arm 2 – CGM Data from each Dexcom device will be downloaded at the end of the blinded phase and analysed. Subsequently, CGM data will be viewed remotely and downloaded.

Finger prick Glucose monitoring diaries will be collected from patients.

Hypoglycaemia questionnaires will be completed with patients

Follow-up procedures

Patients with confirmed hypoglycaemia will remain under standard endocrinology follow up irrespective of whether they choose to partake in arm 2 of the study.

Patients completing arm 2 will remain under standard endocrine follow up at St Bartholomew's hospital, unless they decide to transfer their care elsewhere.

Participant withdrawal

Participants may withdraw at any time. Any data that has been collected up to that point will be retained.

End of study definition

The end of the study (specifically - the end of collecting new CGM data) for each individual patient will be when,

- Arm 1 – The patient completes the inpatient CGM monitoring period and are found not to have hypoglycaemia, OR they complete the inpatient CGM monitoring period, are scheduled for anti hypoglycaemic treatment but do not wish to proceed to arm 2 investigations.
- Arm 2 – The patient completes the initial blinded monitoring phase and analysis shows that no further drug titration is required OR the patient goes into the subsequent unblinded monitoring phase and drug titration abolishes most/all of the hypoglycaemic episodes OR the 30 days of CGM monitoring elapses – whichever occurs first. Patients will be asked to complete a

hypoglycaemia questionnaire prior to surgery to cure hypoglycaemia, or at 6 months after the start of arm 2.

10. Assessment and management of risk

11. Safety Information

Adapted From Dexcom's website <https://www.dexcom.com/safety-information>

Our annotations are in bold, italics and underlined

Dexcom G6 Continuous Glucose Monitoring System

Indications for Use

The Dexcom G6 Continuous Glucose Monitoring System (Dexcom G6 System) is a real time, continuous glucose monitoring device indicated for the management of diabetes in persons age 2 years and older.

The Dexcom G6 System is intended to replace fingerstick blood glucose testing for diabetes treatment decisions. Interpretation of the Dexcom G6 System results should be based on the glucose trends and several sequential readings over time. The Dexcom G6 System also aids in the detection of episodes of hyperglycemia and hypoglycemia, facilitating both acute and long-term therapy adjustments.

The Dexcom G6 System is also intended to autonomously communicate with digitally connected devices, including automated insulin dosing (AID) systems. The Dexcom G6 System can be used alone or in conjunction with these digitally connected medical devices for the purpose of managing diabetes.

Contraindication

No MRI/CT/Diathermy – MR Unsafe

Don't wear your CGM (sensor, transmitter, receiver, or smart device) for magnetic resonance imaging (MRI), computed tomography (CT) scan, or high-frequency electrical heat (diathermy) treatment.

The G6 hasn't been tested in those situations. The magnetic fields and heat could damage the components of the G6, which may cause it to display inaccurate G6 sensor glucose readings (G6 readings) or may prevent alerts. Without G6 readings or alarm/alert notifications, you might miss a severe low or high glucose event.

Warnings

Don't Ignore Low/High Symptoms

Don't ignore how you feel. If your glucose alerts and readings don't match what you're

feeling, use your blood glucose meter to make diabetes treatment decisions or, if needed, seek immediate medical attention. When in doubt, get your meter out.

NB – we will be blinding patients to their continuous glucose monitoring (except in the latter half of arm 2) and will ask patients to check their finger-prick glucose if they experience hypoglycaemic symptoms.

Don't Use If...

Do not use the G6 if you are pregnant, on dialysis, or critically ill.

NB – pregnant patients or those on renal dialysis will be screened out of our study

Precaution

Avoid Sunscreen and Insect Repellent

Some skin care products, such as sunscreens and insect repellents, can make the plastic used in your G6 crack. Before using your G6, make sure there are no cracks in your receiver, transmitter, and transmitter holder. If you find a crack, please contact Technical Support. Do not allow these skin care products to contact your G6. After using skin care products, wash your hands before touching your G6. If any skin care products get on your G6, immediately wipe with a clean cloth.

Start Up Safety Statements

Warnings

Use Meter During Startup

When you start a new sensor, you won't get any readings or alarm/alerts until you enter your sensor code or two calibrations. Use your meter to make treatment decisions during the 2-hour sensor warmup period.

NB – Patient will be blinded to CGM data (except for latter part of arm 2). Data from the first 2 hours of CGM will be discarded.

Precautions

Use Correct Sensor Code

When you start a new sensor, you must enter a code into your display device to use the G6 without fingerstick calibrations. Each sensor has its own code printed on the back of the adhesive patch. Do not use a code from a different sensor or make up a code. If you do not enter the correct code, your sensor will not work as well and could be inaccurate. If you lost the sensor code, you may calibrate the G6 using fingersticks.

Calibration Safety Statements

Calibration is not required if users enter a sensor code. If users do not enter a sensor code, the following warnings and precautions apply.

Warnings

Don't Wait – Calibrate!

If you have not used the calibration code, you must manually calibrate your G6 using

values obtained from a blood glucose meter and fingersticks daily. You must calibrate immediately when the G6 notifies you. If you haven't calibrated when notified, your G6 may not be accurate, so use your glucose meter to make treatment decisions until you calibrate your G6.

Use Fingersticks

Use fingertips to calibrate from your BG meter. Blood from other places may be less accurate and not as timely.

Precautions

Be Accurate, Be Quick.

Enter the exact BG value displayed on your meter within five minutes of using your meter. Don't enter the G6 reading as a calibration.

System/Hardware/Software Safety Statements

Warnings

Wire Breaks Off

Don't ignore broken or detached sensor wires. A sensor wire could remain under your skin. If this happens, please contact our 24/7 Technical Support.

If a sensor wire breaks off under your skin and you can't see it, don't try to remove it. Contact your HCP. Also seek professional medical help if you have symptoms of infection or inflammation – redness, swelling, or pain – at the insertion site.

Where to Insert: Belly or Buttocks?

All patients can use their bellies (abdomen). Patients 2 to 17 years old can also choose their upper buttocks. Look for a place on your belly or upper buttocks where you have some padding.

The sensor is not tested or approved for other sites. Talk to your HCP about the best site for you.

Where to Store

You can store your sensors at room temperature or in your refrigerator – as long as it's between 36° F and 86° F. Don't store sensors in the freezer.

Follow G6 instructions. If you don't, you could have a severe low or high glucose event.

Precautions

Don't Use if Expired

Don't use expired sensors, because they may give incorrect results. Check the package label for the expiration date. It's in YYYY-MM-DD (Year-Month-Day) format.

Check Package

Don't use sensor if its sterile package has been damaged or opened, because it might cause an infection.

Clean and Dry Skin

Clean and dry your hands and your insertion site before inserting your sensor. Wash your hands with soap and water, not gel cleaners, and then dry them before opening the sensor package. If your hands are dirty when you insert the sensor, you may get germs on the insertion site and get an infection. Clean your insertion site with alcohol wipes to prevent infections. Don't insert the sensor until your skin is dry. If your insertion site is not clean and completely dry, you run the risk of infection or the transmitter holder not sticking well. Make sure you don't have insect repellent, sunscreen, perfume, or lotion on your skin.

Where to Insert: Things to Check

Keep the safety guard on until you put the G6 applicator against your skin. If you remove the safety guard first, you may hurt yourself by accidentally pushing the button that inserts the sensor before you mean to.

Change your insertion site with each sensor. Using the same site too often might not allow the skin to heal, causing scarring or skin irritation.

Sensor placement is important. Choose a site:

- At least 3 inches from insulin pump infusion set or injection site
- Away from waistband, scarring, tattoos, irritation, and bones
- Unlikely to be bumped, pushed, or laid on while sleeping

Transmitter Safety Statements

Warnings

Inspect

Don't use a damaged or cracked transmitter. A damaged transmitter could cause injuries from electrical shocks and may make the G6 not work correctly.

Use as Directed

The transmitter is small and may pose a choking hazard. Don't put it in your mouth or let children hold it without adult supervision.

Precautions

Reuse – Don't Throw Away

When ending a session, don't throw away the transmitter. The transmitter is reusable until the G6 notifies you that the transmitter battery is about to expire.

Don't Share

Never share your transmitter. The G6 is a prescription-only medical device and is meant for your use only. The transmitter is tied to the G6 readings. If used by more than one person, the G6 readings, reports, alarm/alerts, etc., may be wrong.

System Safety Statements

Precautions

Treatment Decisions

Use your G6 reading and trend arrow to make treatment decisions.

Use Correct Transmitter, Receiver, and Sensor

G6 components are not compatible with any previous Dexcom products. Do not mix transmitters, receivers, and sensors from different generations.

Going Through Security Check Point

When wearing your G6, ask for hand-wanding or full-body pat-down and visual inspection instead of going through the Advanced Imaging Technology (AIT) body scanner (also called a millimeter wave scanner) or putting any part of the G6 in the baggage x-ray machine.

You can wear the G6 for the walk-through metal detector. If you do, use your meter for treatment decisions until you leave the security area.

Because we haven't tested every x-ray and scanner, we don't know if they damage the G6.

Not sure what kind of machine it is? Be safe – either ask the TSA officer, request hand-wanding, or request full-body pat-down.

Interfering Substance Risks

In previous generations of Dexcom CGM systems (G4/G5), acetaminophen could affect your sensor readings, making them look higher than they really were. However, with the G6, you can take a standard or maximum acetaminophen dose of 1 gram (1,000mg) every 6 hours and still use the G6 readings to make treatment decisions. Taking higher than the maximum dose of acetaminophen (e.g. > 1 gram every 6 hours in adults) may affect the G6 readings and make them look higher than they really are.

Receiver and Smart Device Safety Statements

Precautions

Keep Transmitter Close to Display Device

Keep your transmitter and display device within 20 feet with no obstacles (like walls or metal) between them. Otherwise, they might not be able to communicate. If water is between your transmitter and the display device – for example, if you're showering or swimming – keep them closer to each other. The range is reduced because Bluetooth® doesn't work as well through water.

Get Alarm/Alerts on Display Device You Use

To get your alarm/alerts, set them on the display device you use. Your receiver won't get the alarm/alerts you set on your app. Likewise, your app won't get the alarm/alerts you set on your receiver.

NB – patients will not receive alarms/alerts except for those in the unblinded phase of arm 2.

Is It On?

If the receiver or smart device is turned off (shut down), it will not show G6 readings or alarm/alerts. Make sure your display device is turned on.

Smart Device Safety Statements

Warnings

Check Settings

NB – patients will not receive glucose alarms/alerts except for those in the unblinded phase of arm 2.

When using your smart device, you should confirm that your volume is turned up, your phone is not muted, and you do not have headphones plugged in. If your volume is not turned up, the device is muted, or headphones are plugged in, you will not hear the sound of any notifications, including important alarms. When you have headphones connected to your Android®, alarm/alerts will sound through the headphones and the speaker. On your Apple, they will sound only in the headphones.

Some notifications are silent during the first visual and vibrate notification and then make a sound on the second notification. If you don't clear the alert, it repeats at half volume after 5 minutes and at full volume after 10 minutes.

Your alarm and important alerts sound and display information even when your volume is low or muted. Specifically, if your smart device is on mute, only these notifications make a sound:

Glucose Alarm/Alerts:

- Urgent Low
- Urgent Low Soon
- Low Glucose
- High Glucose
- Rise Rate
- Fall Rate
- No Readings Alert

System Alerts:

- Calibration Required (after 2-hour sensor warmup, only appears when a sensor code is not active)
- Calibration Error (only appears when a user enters a calibration; calibration is not required)
- Sensor Expired
- Replace Sensor
- Transmitter (not working)
- No Storage Error
- App Stopped

There's one exception: On Apple® devices, Signal Loss doesn't sound when your volume is low or muted.

Bluetooth: Your transmitter talks to your app with Bluetooth. Make sure your smart device Bluetooth is on. If not, you will not get alarm/alerts or CGM information.

Notifications:

- Make sure your smart device settings allow Dexcom app notifications to show on your Lock screen. This will allow you to see notifications without unlocking your phone.
